Within SKILLZ-Girl and SKILLZ-Club, our study will examine the additional benefits of offering access to two new health service offerings that are expressly designed to overcome barriers to uptake especially difficult for adolescents to overcome—HIV self-testing (HIVST) kits and access to an expanded method mix for contraceptive methods. Referral for contraceptive and SRH services will be made to the PEPFAR-funded DREAMS Houses or youth corners at local government facilities which are located within close distance to all schools where the SKILLZ package will be implemented.

Our mixed-methods evaluation will assess the effects of the enhanced SKILLZ offering (SKILLZ-Girl Enhanced & SKILLZ Club programs) compared to the SOC SKILLZ offering of SKILLZ-Girl only. Although the SKILLZ Program (Enhanced or SOC pending school allocation) will be offered to all girls enrolled in Grade 10 at selected study secondary schools, only girls aged 16 and over at the commencement of SKILLZ-Girl will be enrolled into the research study.

We will examine outcomes for school girls aged 16 and over enrolled in Grade 10 at the start of the intervention in up to 16 schools where the SOC SKILLZ Package is offered, compared to outcomes in up to 16 schools where the enhanced SKILLZ-Package is offered, including HIVST, the availability of expanded contraceptive services and the SKILLZ-Club following completion of SKILLZ-Girl. Therefore, all schools will be preassigned prior to the intervention into the following 2 categories (see **Figure 3** in *Section 8 - Methodology* below).

1. **SOC:** SKILLZ-Girl → Club SOC
2. **ENHANCED:** SKILLZ-Girl enhanced → SKILLZ-Club

Our central hypothesis is that the additional offering of HIVST and contraceptive services in an enhanced SKILLZ-Girl combined with the SKILLZ-Club offering will increase HIV testing and contraceptive uptake and continuation.

In addition to SKILLZ-Girl and SKILLZ-Club, girls testing HIV-positive at any time during the study intervention period will be additionally offered to participate in the SKILLZ-Plus facility-based curriculum for HIV-infected adolescents. The effect of the SKILLZ-Plus curriculum will be tested using a SmartCare-derived matched (i.e., on clinic, age, ART start date and gender) population.

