- (i) (a) **HIV testing** and (b) SRH-related prevention services uptake among adolescent girls aged 16-19 in up to 9 intervention schools (with enhanced HIVST, PrEP, and contraceptive method offerings) compared to up to 9 control schools using a quasi-experimental difference-in-difference approach; and
- (ii) **linkage to care and treatment, and viral load suppression and retention at 6, 12, and 24 months** through a cohort model using pre-existing SmartCare data on HIV+ individuals in care to match to adolescent girls aged 16 and over from the same district (Lusaka) who are identified to be HIV+ at any time during SKILLZ Girl or SKILLZ Club participation and enrolled in SKILLZ-Plus.

This will be achieved by i) using a quasi-experimental difference-in-difference approach that compares girls aged 16 and over in 9 SKILLZ control schools compared to 9 schools where enhanced SKILLZ will be delivered with the enhanced HIVST and a variety of contraceptive method offerings; and ii) through a cohort model using pre-existing SmartCare data on HIV+ individuals in care to match to adolescent girls aged 16 and over from the same district (Lusaka) who are identified to be HIV+ at any time during SKILLZ-Girl or SKILLZ-Club participation.

Aim 2: Examine how the intervention works including lessons learned for future implementation by

- (i) conducting a process evaluation to identify mediators, predictors, and barriers to uptake of the SKILLZ-Girl, Club, and Plus curricula both quantitatively through mediation and moderation analyses and qualitatively through a sequential explanatory approach using focus groups discussions, interviews and observation with coaches and girls; and by
- (ii) monitoring fidelity

Aim 3: Estimate the short- and long-term cost-effectiveness and return on investment of the SKILLZ Girl, Club, and Plus curricula for improving health outcomes for adolescent girls.

8. Methodology

a. Study design

We will conduct a mixed-methods evaluation of the SKILLZ intervention using the following approaches:

A **quasi-experimental cohort** of school-aged 16-year old and over females to be followed for a two-year period will be evaluated with a difference-in-difference (DID) approach to estimate HIV testing uptake and sexual/reproductive health services use. Primary and secondary outcomes will be measured at several

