Economic evaluation: We will estimate the short- and long-term cost-effectiveness and return on investment of SKILLZ for improving health outcomes for adolescent girls.

Figure 2. Evaluation enrolment flow

b. Study site and population/Research materials

Lusaka is the capital and the most inhabited city in Zambia. Home to 2 million people, it has the highest HIV prevalence at 14%⁴. The study will take place across all the highly densely populated areas of Lusaka where

[figure not shown]
CIDRZ supports government MoH clinics with ARV services, electronic data management, and youth-friendly trained clinical personnel, and where GRS has been implementing their basic curriculum and events. All schools selected will be secular government schools. Approximately 80% of school-age girls are reported to be in school in Lusaka. To facilitate the evaluation of SKILLZ, all girls enrolled in up to 18 government secondary schools in Urban Lusaka that GRS currently serves will be eligible to participate in the SKILLZ program and will be randomly allocated to either the enhanced or SOC SKILLZ implementation. For measuring impact, only girls aged 16 and over enrolled in Grade 10 at the start of the intervention period will be surveyed and followed because youth aged 16 and over can consent for SRH/HIV services without additional parental permission⁵⁵. (See *Section 9: Ethical Considerations* for details on waiver of parental consent).

c. Selection of participants, sampling methods and sample size

Study Population: In each school, we will recruit all girls in Grade 10 who are at least 16 years old at the start of the intervention period (i.e., the commencement of SKILLZ-Girl). Of the 30,000 youth in Lusaka that have benefitted from GRS services to date, GRS has seen HIV testing uptake of 62% as compared to a baseline of 13% (internal program data). We have powered the sample for our primary endpoints in Aim 1ii to account for attrition anticipated along the cascade (see below). For HIV testing, all eligible girls (estimated to be an average of 100 girls per school) in up to 18 schools is large enough to detect a significant difference in testing uptake if setting statistical significance at $\alpha=0.05$, $\beta=0.2$, ICC=0.1, and an expected testing uptake of 60% (control) and 80% (intervention).

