Cluster randomized controlled trial: We will select up to 18 (2 pilot + 16 for full implementation) schools from the Urban District of Lusaka to receive the SKILLZ-Girl curriculum. Of the total (up to 18), half will be randomly allocated to host the standard SKILLZ-Girl curriculum, and the remaining half (e.g., up to eight) will be randomized to either enhanced SKILLZ-Club. Those schools randomized to standard SKILLZ Girl curriculum will only have access to SOC clubs. Those schools selected for enhanced SKILLZ Girl curriculum will offer SKILLZ Club. See **Figure 3** for study allocation flow.

Figure 3. School Selection Flow Chart

[figure not shown]
ONGOING REFERRAL TO COMMUNITY CARE FOR SERVICES

We anticipate that most of our evaluation cohort will not be HIV-infected. Thus, the retention to SRH analysis drives the sample size calculation of 351 girls using contraception at the end of two years, with, and risk ratio difference of 0.3 (30%) between the SOC and enhanced SKILLZ-Club schools. To realize the 351 needed to meet requirements for estimate sensitivity, we augment the initial sample size receiving the SKILLZ-Girl curriculum accounting conservatively for 25% uptake of SRH methods and multiplying by two to assess the difference within each SKILLZ-Girl model (phase 1) and accounting for attrition across the two years of follow-up (12.5%) resulting in a starting sample size of 3159 $((351/0.25) \times 2) \times 1.025$. **SKILLZ-CLUBS** will act as an extension to the SKILLZ-Girl curriculum enabling participants to seamlessly transition from the SKILLZ-Girl curriculum into the SKILLZ-Club. We anticipate minimal attrition (~15-20%). Participants will spend the majority of the study window in SKILLZ-Club and it is through the SKILLZ-Club affiliation that we will follow-up and ascertain outcomes for those enrolled longitudinally.

For the small minority of girls found to be HIV-infected across all schools where the study will be conducted, we will evaluate linkage to care and on treatment, VLS, and retention in care for a period of two years. These girls will be encouraged to continue on to the HIV positive-specific SKILLZ-Plus facility-based curriculum. We will quantitatively measure the impact of SKILLZ-Plus on linkage to care and treatment, retention and viral load at 6, 12, and 24 months after diagnosis (or since participant is identified by GRS as HIV+) using SmartCare data and compare to an existing matched cohort.

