Difference-in-difference model. The primary outcome is the probability of testing for HIV at any time during the period when SKILLZ is delivered through to 24 months after the final soccer event. The primary analysis for Aim 1 will follow a difference-in-difference (DID) effect between study arms. The outcome of interest will be regressed on an indicator of study arm assignment interacted with a dichotomous variable POST which indicates the outcome after the intervention is implemented; this differentiates baseline and end-line for each study arm, controls for any time dependent variables that might confound the effect, as well as any time-invariant observed or unobserved confounders that might differ between study arm schools. Because of this, the DID is robust to time-invariant unobservable confounders (e.g., school quality) and time trends (e.g., secular increase in testing). Our estimator relies on the assumption of common time trends across intervention and control in absence of the intervention, and of static population. Additionally, we control for baseline individual and school-level moderators that may be unbalanced at baseline after randomization. School-level controls include size, promotion rates, sex composition and repetition and dropout rates (available in the district education office) and individual girls' controls include age, grade, maternal education, HIV knowledge. Clustering by school will be accounted for by a generalized estimating equation approach. We will estimate intention-to-treat (ITT) by including all girls in the evaluation cohort assigned to each arm rather than all girls who actually participated in SKILLZ.

Individual-level matched cohort analysis for HIV-infected: The analysis will follow an individual ITT estimator among individuals found to be HIV-infected, who will then be matched (based on clinic, age, ART state date, and gender) to HIV-infected individuals in the SmartCare database. The outcomes are the proportion of enrolled HIV+ girls who linked to care, who are virally suppressed and retained in care at 6, 12, and 24 months after diagnosis of HIV+ (using national electronic HIV medical record data). We will conduct an ITT analysis for the logistic probability of being suppressed at 6, 12, and 24 months after HIV+ diagnosis, where girl is the unit of analysis. All data will be analyzed using STATA.

Process evaluation: This will involve quantitative and qualitative analyses:

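### The primary arm-by-POST test is left to an unspecified GEE on 16 to 18 schools; run in its ordinary form, the nominal 5% test has a size of about 8.8% or 8.3%

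*Combined protocol and SAP*

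**What the plan says.** Section 8f (Data analysis plan, Difference-in-difference model) regresses HIV testing on study arm interacted with POST, adds school-level and individual controls, and analyses by intention to treat. Its whole provision for clustering is: "Clustering by school will be accounted for by a generalized estimating equation approach". On software it says "All data will be analyzed using STATA", which names a package and leaves the options open. Robust and bootstrapped standard errors appear later in 8f, but only for the mediation analysis.

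The number of clusters is small. Section 8c states "We will select up to 18 (2 pilot + 16 for full implementation) schools from the Urban District of Lusaka", and Aim 1 in section 7 describes "using a quasi-experimental difference-in-difference approach that compares girls aged 16 and over in 9 SKILLZ control schools compared to 9 schools". Section 4 differs, with outcomes compared "in up to 16 schools where the SOC SKILLZ Package is offered, compared to outcomes in up to 16 schools", which implies up to 32. The power statement in 8c relies on "all eligible girls (estimated to be an average of 100 girls per school) in up to 18 schools", with ICC 0.1, alpha 0.05, beta 0.2, and testing uptake of 60% in control and 80% in intervention schools.

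**The concern.** The interaction compares school-level changes between two groups of 8 or 9 schools. About 100 girls per school does not add to the 14 or 16 degrees of freedom for that comparison. With so few clusters ordinary GEE inference has two faults that act in the same direction. The sandwich variance is biased downward, because residuals are measured from fitted arm means. The normal reference also ignores the uncertainty of a variance estimated from a handful of schools.

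The true error rate of the primary test therefore depends on choices that 8f does not make and that could be made after the data are seen. Section 1b ties integration into public schooling to the programme proving effective, so a test that is too liberal bears directly on that decision.

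**Working it through.** **Inputs.** From the documents: 16 or 18 schools (8c, section 7) or 32 (section 4), allocated 1:1; 100 girls per school, ICC 0.1, alpha 0.05, 60% against 80% (8c). Assumed: a two-sided test, because sidedness is not stated, and equal school sizes in the closed form. Let *m* be schools per arm and *K* = 2*m*.

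**The plan's own figure.** Two proportions, normal approximation: n per arm = [1.96 × √(2 × 0.7 × 0.3) + 0.8416 × √(0.24 + 0.16)]² / 0.20² = [1.270 + 0.532]² / 0.04 = 81.2, so 82. Design effect = 1 + 99 × 0.1 = 10.9. Then 82 × 10.9 = 893.8 girls per arm, or 8.94 schools, rounded up to 9. This reproduces 18 schools, with about 81% power on a normal reference. There is almost no slack.

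**Size of the ordinary GEE test.** With equal school sizes the arm-by-POST estimate is a difference between two means of school-level change. The uncorrected sandwich has expectation (*m* − 1)/*m* times the true variance, so rejecting when the statistic exceeds 1.96 in absolute value has size

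P( absolute value of t(K−2) > 1.96 × √((m−1)/m) ).

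At 16 schools: 1.96 × √(7/8) = 1.833 on 14 df, giving 8.8%. At 18: 1.96 × √(8/9) = 1.848 on 16 df, giving 8.3%. At 32: 1.96 × √(15/16) = 1.898 on 30 df, giving 6.7%. Interval coverage is the complement: 91.2%, 91.7% and 93.3%.

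**Partial corrections**, by the same formula with the threshold changed:

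| Variance and reference | 16 schools | 18 | 32 |
|---|---|---|---|
| Uncorrected, normal | 8.8% | 8.3% | 6.7% |
| K/(K−1) multiplier, normal | 7.9% | 7.5% | 6.3% |
| Unbiased variance, normal | 7.0% | 6.8% | 5.9% |
| Uncorrected, t(K−2) | 6.5% | 6.3% | 5.7% |
| Unbiased variance, t(K−2) | 5.0% | 5.0% | 5.0% |

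**Simulation check.** 40,000 runs per setting; uncorrected sandwich, normal reference, independence working correlation. Baseline was 13% (programme data in 8c), endline 60% in both arms and ICC 0.1. Assumptions: between-survey school correlation 0, 0.5 or 0.8; school-size coefficient of variation (CV) 0 or 0.4; girls drawn independently at the two surveys.

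| Link, school-size CV | 16 schools | 18 | 32 |
|---|---|---|---|
| Linear, CV 0 | 8.8-9.0% | 8.1-8.6% | 6.7% |
| Linear, CV 0.4 | 9.9-10.1% | 9.5-9.9% | 7.1-7.6% |
| Logit, CV 0 | 9.9-10.5% | 8.8-10.1% | 7.1-7.3% |
| Logit, CV 0.4 | 11.0-11.7% | 10.3-11.0% | 7.8-8.3% |

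The linear, equal-size row agrees with the closed form. A logit link or unequal schools generally makes the inflation larger.

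**What the correction costs.** With equal sizes, Kauermann-Carroll restores the unbiased variance; Mancl-DeRouen gives m/(m−1) times it. The interval width relative to the uncorrected one is (t/1.96) × √(m/(m−1)) for Kauermann-Carroll and (t/1.96) × m/(m−1) for Mancl-DeRouen. With t = 2.145 (14 df) and 2.120 (16 df), this gives 1.17 and 1.15, and 1.25 and 1.22.

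Power on the endline-only inputs of 8c uses a standard error of √((0.24 + 0.16) × 10.9 / (100m)), which is 0.0738 at m = 8 and 0.0696 at m = 9. The noncentrality is 0.20/SE = 2.71 and 2.87.

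| Reference | 16 schools | 18 |
|---|---|---|
| Normal | 77% | 82% |
| t(K−2), unbiased variance | 71% | 77% |
| t(K−2), Mancl-DeRouen | 66% | 73% |

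The pooled-variance normal formula gives 75.8% and 80.7% in place of the first row.

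**The case against.** The strongest reply is that the plan never says it will use an uncorrected sandwich. A corrected GEE would comply with 8f, and many SAPs leave this to the analyst. That stands as a limit on the claim. A reader might infer that this trial's false-positive rate is 8.8%; the documents do not support that, because 8.8% belongs to one permitted implementation. What remains is that 8f permits procedures of clearly different size, and that ordinary GEE followed as written is among the liberal ones.

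A second reply is that the simulations above omit the school-level controls in 8f. In a balanced linear model, time-invariant controls leave the interaction coefficient unchanged. A limited check at 16 schools with five random school covariates (3,000 runs, assumed between-survey correlation 0.5, CV 0 and 0.4) gave 8.8-12.3% uncorrected and 3.5-4.9% with Mancl-DeRouen and t(K−2). The conclusion survives, but that check is small.

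A reader might also infer a much larger error rate from a model-based variance with one exchangeable correlation over both surveys. That variance is unsafe for inference here, but the documents give no basis for a figure. It depends on correlation between surveys at both school and girl level. Neither is stated, and sections 8a and 8d follow the same girls over time. For the same reason the power figures above are not powers for arm-by-POST.

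The conflicting school counts, and whether allocation is randomised, are separate points and are not needed for this one.

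**Conclusion.** The point holds in conditional form and should be fixed. The documents give no small-sample provision for the primary test, which rests on 14 to 16 between-school degrees of freedom. If the uncorrected sandwich is used with a normal reference, false positives at the 5% level occur about 1.8 times (16 schools) or 1.7 times (18) as often as stated. No single half-measure in the first table restores 5%; a bias correction and a t reference are needed together.

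The closed-form figures assume a two-sided test, 1:1 allocation, equal school sizes and roughly normal school-level changes. The simulated range rests on assumed correlations and school-size variation and is not a bound.

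**What to change.** In 8f, state for the arm-by-POST term:

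- the working correlation;
- a small-sample bias-corrected sandwich variance, with Mancl-DeRouen or Kauermann-Carroll chosen before data are seen;
- a t reference on (schools − 2) degrees of freedom;
- that inference will not use a model-based variance from a single exchangeable correlation that ignores the between-survey structure.

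Either correction is defensible. With equal schools Kauermann-Carroll has size 5.0%, while Mancl-DeRouen is conservative at 3.8-3.9% for 16 to 18 schools. Across simulated settings the corrected tests ran at 3.7-6.9%.

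In 8c, restate power with the t reference. On the existing endline-only inputs it is about 77% at 18 schools and 71% at 16, or 73% and 66% with Mancl-DeRouen, against the stated 80%. Say that these are not powers for the interaction.

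The wording and programming are minor. The real costs are 95% intervals about 15-17% wider (Kauermann-Carroll) or 22-25% wider (Mancl-DeRouen) at 16 to 18 schools, and a stated power below target.

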ongoing activity that students can participate in until they leave or graduate from school. Girls participating in the SOC Arm (SKILLZ-Girl) are able to join any of the other clubs currently offered at their school (SOC Clubs).

Clubs have been operating in schools in Zambia since 2017 with the MOGE's consent as part of the Memorandum of Understanding (MOU) signed in 2010 (*see Appendix B*). The CLUB component is currently evolving to include a more formalized education component, and will be piloted in Zambia at the same time as this evaluation.

4. All girls who test positive for HIV (whether prior to the SKILLZ-Girl event, during the event or as part of their participation in SKILLZ-Club) are referred to **SKILLZ-Plus**, a clinic-based initiative which provides HIV-infected girls access to ongoing support through a 12-week curriculum. During follow-up in the SOC Club arm, study staff will refer any newly identified HIV-positive girls to SKILLZ-Plus. In addition, study staff will refer newly diagnosed girls aged 16 years from neighboring clinics to the SKILLZ-Plus intervention.

For girls who test positive for HIV, either through a:

1. school referral either at the event, during club participation, are identified during follow-up or with a previously known diagnosis or
2. clinical referral (newly diagnosed only)

In addition, all girls found to be HIV-positive at any point throughout the SKILLZ-Program will be provided with intensive counselling support. Coaches will facilitate a family visit to facilitate disclosure and work with CIDRZ networks to provide additional psycho-social support as needed on a case-by-case basis by the participant.

SKILLZ-Plus provides several additional features:

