timepoints longitudinally across up to 9 schools offering the enhanced SKILLZ-Girl and SKILLZ-Clubs program and up to 9 schools offering the “standard of care” (SOC) SKILLZ-Girl and SOC Clubs (see Figure 3). Recruitment will take 12 months on a rolling basis. The order in which schools will be selected will be random. Participants will be clustered at the school-level; we will enroll all girls aged 16-years at the commencement of SKILLZ-Girl and in Grade 10 from each participating school.

[figure not shown]
All enrolled girls will be followed over the two-year time period to assess SRH service uptake, including HIV testing. It is estimated that the majority (~98%) of girls testing for HIV will likely be HIV-negative, based on estimates from programmatic GRS data. While HIV-positive girls will continue to participate in the school-based SKILLZ-Girl and Clubs activities and followed for SRH use, they will also be offered contemporaneous enrollment into SKILLZ-Plus upon infection; retention in care and Viral Load Suppression (VLS) at 6, 12, and 24 months will be measured for this subset. See **Figure 2** for details of enrolment flow.

Process evaluation: We will conduct a process evaluation to better understand the casual pathways and effect mediators and moderators using mixed methods approaches, including supplemental qualitative data collection. To investigate reasons why the program components (SKILLZ-Girl, Club & Plus) might fail or succeed in different schools or communities and assess intervention effect mediators and moderators for HIV testing and contraceptive use uptake we will use a mixed methods approach involving: (1) quantitative analyses of baseline survey data for testing how variables can moderate the observed impact of the intervention, and (2) qualitative data collected from a subset of SKILLZ participants in the evaluation cohort and their coaches to further understand potential mediating pathways outlined in Figure 1.

Fidelity monitoring: We will also include measures to monitor fidelity of the intervention implementation, including receptivity to and understanding of the intervention amongst participants, the perceived appropriateness and relevancy of the intervention for adolescent girls in school, and the extent to which the intervention was delivered per protocol in different communities and schools.

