SmartCare electronic data: All antiretroviral therapy services offered as part of the study will be captured in SmartCare, which permits measuring of utilization and clinical outcomes (i.e., Linkage to Care, VLS) at soccer events, mobile clinics, and public clinics in Lusaka. VLS is defined as below detection, i.e. less than 50 copies/ml. Retention in care will also be measured using SmartCare data on pharmacy visits and defined as accessing pharmacy within a 90-day window of visits. Consent will be requested from all participants as part of the consent process to access their SmartCare records.

Youth-Friendly services electronic data: Depending on the location of the school, the girl's residential address and/or her own personal preferences, participants will be referred to either the PEPFAR Funded DREAMS houses or the M.A.C. funded youth-friendly spaces based in local MOH clinics in order to access ongoing SRH services after the events (this will include accessing PrEP, STI testing and contraceptive methods). All interactions with the DREAMS houses or M.A.C centres (including meeting with counselors, referral and uptake of services) are captured in their respective electronic databases. Consent will be requested from all participants as part of the consent process to allow researchers to access either DREAMS or M.A.C data should they chose to access either of these services.

Survey at baseline: A baseline survey will be administered to all to collect information on school characteristics, sexual behavior, age, HIV knowledge, maternal education, baseline HIV status, and sexual/reproductive health uptake and retention. These variables will be used as covariates and moderators for service uptake and retention. The target sample of 3,200 girls will respond to a survey self-administered using REDCap software upon informed consent. The survey will be available in English, Nyanja and Bemba. Coaches and study staff will on site be help girls navigate the survey.

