Survey post-SKILLZ-Girl event, 3-, 12-, and 24 months: All girls (regardless of HIV status) will respond to a REDCap survey to collect information on sexual behavior, HIV knowledge, maternal education, sexual/reproductive health uptake and retention. Post-SKILLZ-Girl survey data will be used to assess the effect of SKILLS Girl and SKILLZ-Club on the outcomes of interest. In schools selected to offer SKILLZ-Club, surveys will be conducted during club attendance approximately 3 months after the SKILLZ-Girl community soccer event; coaches will help them navigate the survey. If a participant has opted to not attend the clubs or has since left or changed schools, the coaches and study staff will attempt to trace participants in the community in order to complete the follow-up survey.

In the schools selected not to offer SKILLZ-Club, GRS will arrange for a 2-hour meeting session with all participants still enrolled at that school, where all participants will complete the surveys. If a participant opts to not attend the meeting or has since left or changed schools, the coaches and study staff will attempt to trace participants in the community in order to complete the follow-up survey.

The survey will record any changes to their home environment from baseline, again ask about self-reported sexual and risk behaviors and HIV knowledge (i.e., post-test for HIV education curriculum), and further quantitatively measure potential mediating pathways. Based on validated scales, the survey will include modules to assess stigma;⁵⁷ empowerment;⁵⁸ and self-efficacy⁵⁹ in general and specific to SRH/HIV;⁶⁰ disclosure, extent of social support from different sources (e.g., family, peers, teachers), and trust in health providers.⁶¹ Individual lost to follow-up (LTFU) will be traced following standard procedures. Active follow up and tracing of late or lost patients enrolled into HIV care or receiving ART is part of the National treatment program. We will partner with pre-existing CIDRZ community volunteers responsible for follow up to ensure that efforts are synchronized, and that data are shared and entered into SmartCare. CIDRZ already has an international reputation leading effort to track those who are lost to ensure participants return for visits and viral load testing as per national guidelines.⁹⁸

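### The primary HIV-testing outcome is analysed in all girls, including those already known to be HIV-positive, for whom not testing again is not a programme failure; the effect is a small dilution.

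*Combined protocol and SAP*

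**What the plan says.** Section 8f, Difference-in-difference model: "The primary outcome is the probability of testing for HIV at any time during the period when SKILLZ is delivered", continuing to 24 months after the last event. The outcome carries no condition on HIV status. The analysis set is equally broad: "We will estimate intention-to-treat (ITT) by including all girls in the evaluation cohort assigned to each arm".

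Section 8c sets eligibility: "In each school, we will recruit all girls in Grade 10 who are at least 16 years old". HIV status is not a criterion. Follow-up in Section 8d is the same: "All girls (regardless of HIV status) will respond to a REDCap survey".

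Section 4, on entry to SKILLZ-Plus, lists school girls who "are identified during follow-up or with a previously known diagnosis", so girls diagnosed before the study are expected in the cohort.

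The baseline survey in Section 8d collects "maternal education, baseline HIV status, and sexual/reproductive health uptake and retention" and assigns these variables to covariate and moderator use. The process evaluation in Section 8f also plans to interact exposure with HIV testing or status. The girl-level controls named for the primary model, however, are HIV knowledge, maternal education, grade and age. HIV status is not among them.

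Nothing in the plan removes known positives from the testing denominator, says how they are scored, or provides a sensitivity analysis.

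**The concern.** The aim is to raise HIV testing. For a girl who already knows she is positive, the score says nothing about that aim: no test is not a failure of the programme, and a repeat test is not the success sought. Section 8a already gives HIV-positive girls outcomes of their own (retention in care and viral suppression, next to SRH use), but the testing outcome does not carry that distinction through.

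Two things are at stake. Uptake and the arm difference are pulled down by roughly the share of known positives. And with few schools, an unequal share between arms enters the contrast. Differencing against baseline need not remove this, because a known positive may have a different change over time and not only a different level. If the rule stays unwritten, someone may have to choose the denominator after the data are seen.

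**Working it through.** **Inputs.** From Section 8c: testing uptake 60% (control) v 80% (intervention), alpha 0.05 (two-sided assumed), power 0.80, ICC 0.1, an average of 100 girls per school, up to 18 schools (9 per arm). From Section 8a: "the majority (~98%) of girls testing for HIV will likely be HIV-negative", so about 2% of those who test are expected to be positive. The share already known positive at baseline is not in the documents. I assume 0.5% to 5%, with 2% as a borrowed anchor.

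**1. The plan's own figure.** Pooled normal formula for two proportions, no continuity correction: 82 girls per arm without clustering. Design effect = 1 + (100 - 1) x 0.1 = 10.9. Required: 82 x 10.9 = 894 girls per arm, or 8.94 schools, against the planned 900 and 9. Power at 900/10.9 = 82.6 effective girls per arm is 80.7%. The stated power reproduces.

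**2. Dilution.** Let f be the share known positive, equal in both arms, with none retesting, and let 60% and 80% apply to the other girls. Observed rates are 0.60(1 - f) and 0.80(1 - f); the difference is 0.20(1 - f).

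| f | control | intervention | difference (points) | power |
|---|---|---|---|---|
| 0 | 60.0% | 80.0% | 20.0 | 80.7% |
| 0.5% | 59.7% | 79.6% | 19.9 | 80.0% |
| 1% | 59.4% | 79.2% | 19.8 | 79.3% |
| 2% | 58.8% | 78.4% | 19.6 | 78.0% |
| 5% | 57.0% | 76.0% | 19.0 | 73.9% |

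If 30% or 60% of known positives retest in both arms, power at 2% is 78.4% or 78.9%. For scale, leaving out the two pilot schools (8 per arm) gives 75.8% with no dilution at all.

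**3. Chance imbalance, end-line contrast only.** With 1% in control and 3% in intervention: 0.80 x 0.97 - 0.60 x 0.99 = 18.2 points. Reversed: 0.80 x 0.99 - 0.60 x 0.97 = 21.0 points. At 2%, 900 girls per arm and no clustering of HIV status, the SD of the arm difference in f is sqrt(2 x 0.02 x 0.98/900) = 0.66 points; clustering would enlarge it. The standard error of the arm difference in testing is sqrt((0.24 + 0.16)/82.6) = 7.0 points.

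**4. In the difference-in-difference model.** The plan does not define the baseline testing outcome, so three cases are open for a known positive who does not retest:
- Ever tested at baseline, tested within the window at follow-up: she goes from 1 to 0, a change of -1.
- Ever tested at both times: 1 and 1, a change of 0.
- A recent window at both times, diagnosis older than that: 0 and 0, a change of 0.

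In the first case, take other girls' baseline as 13% (Section 8c, programme data) or 47.5% (Section 1a, girls aged 15-19). Their mean change runs from 0.60 - 0.475 = 0.125 to 0.80 - 0.13 = 0.67. The gap to -1 is 1.125 to 1.67, so each 1-point imbalance moves the estimate by about 1.1 to 1.7 points. In the other two cases the shift is smaller.

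**5. With known positives excluded at 2%.** 98 girls per school, 60% v 80%: 882/(1 + 97 x 0.1) = 82.4 effective girls per arm, power 80.6%.

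**The case against.** Four points on the other side carry weight.

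- A reader might infer that known positives can only count as failures. The documents do not support that. Any test in the window counts, Section 4 describes the offer of testing at the event or a take-home kit without a status restriction, and nothing bars a girl with a diagnosis from testing. Non-testing is likely, not certain. Girls first diagnosed during the study count as testers and are unaffected.
- A reader might infer bias between arms. Sections 8b and 8c allocate schools at random, so equal shares are expected and the effect is conservative dilution. Imbalance is chance, and a 1-point imbalance moves the estimate by under 2 points against a standard error of about 7.
- Baseline status is foreseen as a covariate or moderator, and Section 8f speaks of controlling for baseline moderators that turn out unbalanced. This stands as far as it goes. But status is missing from the named controls, and adjustment would leave the denominator as it is.
- An all-girls analysis suits a pragmatic trial, and the planned 60% and 80% may already be all-girl rates. If so, the planned power holds as stated; excluding 2% would then give 61.2% v 81.6% and 83.3% power. This is a reason to keep the all-girls result in the report, not to leave the rule unwritten.

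The change of -1 in step 4 is also not specific to known positives. Under that mixed definition, any previously tested girl who does not retest would score the same. That gap in the baseline definition is separate and probably larger.

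**Conclusion.** The point holds as a minor one. Known HIV-positive girls are in the denominator of the primary testing outcome, their score is uninformative about the aim, and the plan has no rule for them although it collects the variable needed.

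At an assumed 2% with no retesting, the cost is 0.4 points of difference and about 2.7 points of power (80.7% to 78.0%). Over 0.5% to 5%, power runs from 80.0% to 73.9%. These figures rest on the assumed share, on no retesting, and on 60% v 80% applying to girls not known positive. The 2% must not be read as a documented figure or an upper bound for known positives: it is the positive share expected among girls who test. The size of any imbalance effect in the difference-in-difference model cannot be fixed until the baseline testing outcome is defined. None of this threatens the trial's conclusion, and the point takes no position on whether girls with a diagnosis should be retested.

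**What to change.** In Section 8f, Difference-in-difference model, define the HIV-testing analysis population as girls not known to be HIV-positive at baseline, in both arms. Report the all-girls intention-to-treat result alongside. Keep known positives in the contraceptive and SRH outcomes.

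A diagnosis that predates the programme cannot be caused by the arm, so the restriction preserves the randomised comparison. State that status is taken as recorded at the baseline survey and is not updated later, so that girls diagnosed during the study remain in.

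The cost is one added rule and a few girls in one analysis: 0.02 x 1,800 = 36 at 2%, with power at 80.6%, practically the planned level. The real drawback is reliance on self-reported status. Undisclosed positives stay in, and disclosure could differ between arms if girls know their school's allocation when surveyed. Checking against SmartCare, for which consent is already sought (Section 8d), would limit this where consent is given.
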